DXA, CT scans and Muscle Composition Assesment: Using methods developed in our previous studies total and regional % body fat, fat mass, lean tissue mass, and bone mineral content will be determined by DXA. CT scans will be performed of the abdomen, hips, and thighs using a Siemens Somatom Sensation 64 Scanner. Three CT scan slices will obtained; one at L3-L4, one at the level of the mid-thigh and the third proximal to the caput femoris. These scans will be used to quantify muscle composition and muscle attenuation for the primary hip flexors and extensors, abductors and adductors, and for the knee flexor/extensors. The cross-sectional area of the slice as well as the specific muscle group will be manually outlined as a region of interest

and muscle composition as indexed by muscle attenuation will be calculated. We hypothesize that veterans at increased fall risk will have sarcopenia and dynapenia. Training should increase muscle mass and improve muscle quality as indexed by less fat infiltration in muscle.

AIM 2 Exploratory Outcome Measure: number of falls, near falls, injuries and fall related medical visits. We will determine if there is a difference in our interventions in preventing the number of falls, near falls, injuries and fall related medical visits during the 6 month intervention. During the intervention period individuals will be instructed to call the study coordinator to report any details of all falls and near falls within 24 hours of the occurrence after enrollment into the study. The study coordinator will collect all details of the fall and near fall including the location, the activity, and hazards that may have precipitated the loss of balance, and any injuries and medical care that was required. Participants will additionally be asked at each exercise session if any falls or near falls have occurred. After the completion of the intervention all participants will be given monthly pre-stamped post cards to report any falls or near falls that may occur. The study coordinator will phone each participant monthly to follow up on any fall incidence. We have employed similar methodology in a number of studies.

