#### Sample Size Determination and Power Analysis

This is a pilot study with an aim towards developing estimates for effect sizes that can be used to design a larger, confirmatory randomized clinical trial. A sample size of 20 per group will allow us to detect a difference of 25% between groups for our primary outcome of the four square step test. We will enroll 40 subjects. Typical attrition rates are 25 to 30%, primarily due to time conflicts and development of non-study related medical problems. In our preliminary studies, MMBI decreased the time to complete the four square test by 24%, with even greater improvements in the frailest subjects. Time to complete the four-square test has been shown to be an excellent biomarker for fall risk.

For our second exploratory Aim the outcome will be the rate of falls and the proportion of fallers during the intervention. The sample size estimate is determined primarily by three factors; the baseline rate of falls in the study population, the duration of follow-up, and the differential impact of the two interventions on the fall rates. For example in the Lifestyle integrated Functional Exercise (LiFE) program, which embedded balance and lower limb strength training into habitual daily routines there was a statistically significant 31% reduction in fall rates (1.66 per person years) compared to controls (2.28 per person years), whereas the structured lower limb strength and balance exercises had a non-significant 19% reduction (1.90 per person years) in fall rate compared with the controls. Based on this and other literature we estimate that setting the power at 80%, alpha at 5% and with a drop-out rate of 20%, a sample size of 90 is required in each group to detect a clinically significant difference of 25% reduction in falls frequency between the two groups. Due to the budgetary limitations and duration of this VA SPIRE grant it is not feasible for us to enroll and study 180 subjects. Thus we recognize that we might not have sufficient power to see a difference in fall rate and number of falls between groups. Results from this study will be used to power a larger randomized clinical trial that will examine the effectiveness of the two interventions to reduce rate of falls and risk of falling in older veterans at high risk for falls.

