Statistical Analysis: Data analyses will be performed using SAS. We will first perform an exploratory analysis to look for extreme values to make sure they are not the result of data entry error. All analyses will be conducted using the intention-to-treat principle. Statistical significance will be at an alpha of 0.05 (two-tailed). Demographic and clinical characteristics at baseline will be summarized with standard descriptive statistics.

For aim 1, to compare changes (defined as 24-week value minus baseline value) in mobility, balance and strength between our two groups (tai chi and MMBI) after 24 weeks of intervention we will use ANOVA for all continuous outcome measures (change=group).

For Aim 2 We will use Poisson regression (or, if the data are overdispersed Quasipoisson or negative binomial regression) to compare the number of falls in our two experimental groups. This methodology has been employed in the LiFe trial and other studies.

Project time line: Prior to the start of the funding, we will obtain regulatory approvals from the IRB and VA R&DC. We will recruit 3 sets of intervention cohorts. Recruitment and baseline testing of the first cohort will start at the start of the funding period and they will enter intervention at month 3. While this first cohort is undergoing intervention we will recruit and perform baseline testing on the second cohort who will enter the intervention approximately 6 months after the start of the study. Post intervention testing on the first cohort will commence at 9 months. Recruitment for the third cohort will be done while the second cohort is in intervention and the third cohort will start their intervention at 9 months. During months 21 to 24 we will perform data analysis, and start writing manuscripts. We have used a similar strategy of staggered cohorts in prior studies. The study will be completed in a two years.

Anticipated Results and Alternate Findings: While we do not anticipate that Tai Chi will result in larger improvements in balance and falls than MMBI it is possible. The strength, balance, and gait tests that we are performing allow us to evaluate the contribution each makes to improving balance. This information can be used to design a future larger study aimed at decreasing falls.

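### Aim 2 names a fall rate as its outcome but models a fall count with no exposure term, so unequal lost observation time between arms would bias the comparison

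*Combined protocol and SAP*

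**What the plan says.** The combined protocol and SAP describes the Aim 2 quantity in three places, and they do not agree.

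- **Sample Size Determination and Power Analysis:** "the outcome will be the rate of falls and the proportion of fallers during the intervention". The LiFE trial results quoted there as a benchmark are per person-year.
- **Aim 2 outcome paragraph:** "AIM 2 Exploratory Outcome Measure: number of falls, near falls, injuries and fall related medical visits". This is a count.
- **Statistical Analysis:** Poisson regression, or quasi-Poisson or negative binomial if the data are overdispersed, "to compare the number of falls in our two experimental groups". It adds: "This methodology has been employed in the LiFe trial and other studies".

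No offset, exposure term or person-time is stated in any section. The analysis is by intention to treat, with no rule for partly observed participants, and no method is given for the proportion of fallers.

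On loss, the sample-size section says: "Typical attrition rates are 25 to 30%, primarily due to time conflicts and development of non-study related medical problems". On fall follow-up, the Approach paragraph has everyone followed from enrolment until 6 months after post-intervention testing, by diaries, postcards and monthly calls. The Aim 2 outcome paragraph describes the intervention phase differently: participants phone in falls and are asked at each class, and postcards and monthly calls are described after the intervention ends.

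**The concern.** A count and a rate lead to the same between-arm comparison only when the arms are observed for the same average time. With a quarter or more of participants expected to leave, individual observation time is likely to vary. An analyst who follows the Statistical Analysis paragraph literally would regress falls on group alone. Any difference in lost time between the arms would then be read as a difference in fall risk, in favour of the arm that lost more.

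The stakes are modest but real. Aim 2 is exploratory and the plan admits that it lacks power. However, the sample-size section says the results will be used to power a larger trial on fall rates, so a distorted ratio would be carried forward.

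**Working it through.** **The plan's own figure.** The only Aim 2 calculation is 90 per group (80% power, 5% alpha, 20% drop-out) "to detect a clinically significant difference of 25% reduction in falls frequency between the two groups". The base rate and follow-up behind it are not given. If the LiFE control rate of 2.28 per person-year and 12 months are assumed, with two-sided 5%:

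n = (1.96 + 0.842)² × (1/2.28 + 1/1.71) / (ln 0.75)² ≈ 98, and about 122 after dividing by 0.8.

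Six months gives 243. The 90 therefore cannot be checked from the stated inputs, and nothing below depends on it.

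**Inputs for the bias**
- Attrition 25 to 30%, one range for both arms (sample-size section).
- MMBI pilot: 16 of 17 completed, so 1/17 = 5.9% lost (Preliminary Studies; 16 weeks, single arm).
- Assumed: equal true fall rates, equal numbers randomised, loss unrelated to fall risk, and withdrawers observed for a mean fraction f of the period. The documents do not give f, so a range is shown.

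**Formula.** If a share d of an arm withdraws, its mean observed fraction is 1 − d(1 − f). With no offset, the expected Tai Chi/MMBI count ratio is

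R = [1 − d_T(1 − f)] / [1 − d_M(1 − f)].

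| Loss, MMBI v Tai Chi | f = 0 | f = 0.25 | f = 0.5 | f = 0.75 |
|---|---|---|---|---|
| 25% v 25%, or 30% v 30% | 1.00 | 1.00 | 1.00 | 1.00 |
| 25% v 30% | 0.933 | 0.954 | 0.971 | 0.987 |
| 5.9% v 25% | 0.797 | 0.850 | 0.902 | 0.951 |
| 5.9% v 30% | 0.744 | 0.811 | 0.876 | 0.939 |

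Two entries written out:
- 25% v 30%, f = 0.5: 0.850/0.875 = 0.971, so 3% too few falls in Tai Chi. At f = 0.25, 0.775/0.8125 = 0.954, so 5%.
- 5.9% v 30%, f = 0.5: 0.850/0.971 = 0.876, so 12%.

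In the last case a true MMBI/Tai Chi ratio of 0.75 would appear as 0.75/0.876 = 0.86. If the losses were reversed, the same bias would favour MMBI.

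**With the offset.** Dividing by observed time returns a ratio of 1.00 in every row. A simulation (40,000 replicates, Poisson Wald test, 2.28 falls per person-year, 20 or 28 per arm, uniform withdrawal times) gave these type I error rates:

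| Scenario | No offset | Offset |
|---|---|---|
| 5.9% v 30%, 6 months | 7.4 to 8.5% | 4.8% |
| 5.9% v 30%, 12 months | 10.7 to 12.5% | 4.9% |
| Equal loss, 25% or 30% | 5.5 to 7.3% | 4.4 to 5.0% |

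The excess under equal loss comes from uneven exposure within arms. The plan's overdispersion fallback is aimed at that kind of excess and was not simulated, so I put little weight on it.

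**Proportion of fallers.** Take 1.90 falls per person-year (a LiFE rate, assumed here) and a Poisson process. The chance of at least one fall is 1 − exp(−0.95) = 0.613 over 6 months and 1 − exp(−0.475) = 0.378 over 3 months. If withdrawers leave halfway and are counted on what was observed, then:
- 25% loss: 0.75 × 0.613 + 0.25 × 0.378 = 0.554.
- 30% loss: 0.70 × 0.613 + 0.30 × 0.378 = 0.543.

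The ratio is 0.98.

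**The case against.** The strongest reply is that a rate analysis was intended and only the offset is unwritten. The sample-size section names a rate, its benchmarks are per person-year, and the Statistical Analysis paragraph points to LiFE for its method. This stands as to intent: it would be wrong to say that the plan ignores observation time altogether. It does not supply the model, because the method actually described is a regression on the number of falls.

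Three stronger readings are tempting, and the documents do not support them.

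- *Every withdrawal lowers its arm's count.* All participants are to be followed for falls, so stopping class need not end surveillance. Some loss is still plausible: those who stop attending lose the per-class question, and anyone who misses post-intervention testing has no defined end of follow-up.
- *The plan predicts unequal retention.* Aim 1 H2 predicts better adherence with MMBI, which is not the same as retention, and the expected attrition is one range for both arms. The pilot's 1 in 17 makes unequal loss conceivable, not expected.
- *The proportion of fallers would be 61% against 38%.* Those are one person's chances over 6 and 3 months, not a contrast between arms. The arm-level effect at 25% v 30% loss is about 2%.

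Sampling error is also far larger than the bias. At 20 per arm, 1.90 falls per person-year and 6 months, each arm expects 19 falls. The standard error of the log ratio is √(2/19) = 0.32, so the 95% limits span a factor of about 1.9 either way. That limits the practical effect in this pilot, but it is no reason to keep an avoidable bias in the estimate.

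**Conclusion.** The point holds as a mismatch between the named outcome and the stated model. The outcome is a rate, the model is for a count, no exposure term links them, and loss of a quarter or more is expected. Directional bias needs two further conditions: withdrawal must shorten fall observation, and the lost time must differ between arms.

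Where both hold, 25% v 30% is the widest gap inside the plan's own attrition range, and it gives 3 to 5% for f between 0.25 and 0.5. The 12% figure requires a 16-week pilot's loss to carry over to MMBI while Tai Chi sits at the top of the range, with f = 0.5; varying f from 0 to 0.75 moves it between 26% and 6%. All these figures assume equal true rates and loss unrelated to fall risk.

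This is a free improvement to an exploratory aim, not a threat to the trial's main conclusions.

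**What to change.** In the Statistical Analysis paragraph for Aim 2:

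1. Add log(person-time under fall surveillance) as an offset to the Poisson, quasi-Poisson or negative binomial model, and report a rate ratio with its confidence interval. Align the Aim 2 outcome paragraph with this.
2. For the outcome named in the sample-size section, count person-time from randomisation to the earlier of the end of the intervention period and the last completed fall contact, for all randomised participants. Count falls over the same window.
3. Analyse the 6-month post-intervention follow-up as a separate window with its own offset. Running person-time straight through to the last contact would estimate something other than the rate during the intervention.
4. Analyse fallers as time to first fall, censored at the same date, or with a complementary log-log model and the same offset.
5. State that this assumes loss of follow-up is unrelated to fall risk. The offset does not correct for participants who leave because their health, and so their fall risk, has changed; the plan expects some medical withdrawals.

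The cost is SAP wording. The dates come from coordinator contacts already planned, provided contacts with no fall to report are also dated. No extra patients or visits are needed, and if follow-up turns out to be complete the offset does no harm.
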